### 5.8 Subgroup analyses

The main analysis for the primary endpoint and each secondary endpoint will be presented for the following subgroups:

- geographic region (North America, Europe and Asia-Pacific).
- below and above the stratification factor used in the randomization (Age at screening < 6 years versus  $\geq 6$  years)
- Disease duration (time from SMA onset to Screening in months) by tertiles

The difference between treatments for continuous endpoints and the proportion of responders in each treatment group and the odds ratio for the binary endpoints will be presented.

If the number of subjects in a subgroup is too small (e.g., < 15% of total number of subjects in the ITT population), the analysis in that subgroup may not be performed. In the event an interim analysis is performed then subgroup analyses will be performed but the number of subjects with a Month 15 value within a subgroup will be assessed and if <40% of subjects have a Month 15 value then these may not be presented. No statistical tests will be performed in the subgroups.

It is anticipated that 8 subjects will be enrolled in Japan and a separate set of tables and listing will be presented for Japanese subjects.

## **5.9 Unblinding Plan for the Interim Analysis**

The interim analysis will be performed by a contract research organization (Parexel) and reviewed by an independent Data and Safety Monitoring Board (DSMB) overseeing the study and an Unblinded Senior Management Team from the sponsor. The DSMB, in accordance with its Charter, will make a recommendation to the study Sponsor on whether or not the study should continue according to the protocol or any modifications are needed based on the emerging benefit/risk profile.

After the review of the interim analysis results the Unblinded Senior Management Team will decide whether or not to proceed with regulatory submissions. This decision will be based on totality of the data including the overall consistency of the data and the benefit/risk assessment. If the Unblinded Senior Management Team decides to continue the study without regulatory submission, no additional personnel from the Sponsor will be unblinded to the interim data. Should the Unblinded Senior Management Team decide to proceed with regulatory submissions, an internal filing team will be unblinded to the interim data. The internal filing team will prepare and submit the marketing applications to the regulators. Members of both the Unblinded Senior Management Team and the internal filing team will not be involved with study management or operations after being unblinded to the interim data. All internal individuals who had access to the unblinded interim data will no longer be involved in the conduct of the blinded study.

## 6 Safety data

Analyses of safety data will include adverse events and serious adverse events ([Section 6.1](#)), laboratory data ([Section 6.2](#)), ECGs ([Section 6.3](#)), vital signs ([Section 6.4](#)), and neurological examinations ([Section 6.5](#)). Any worsening or new findings noted from the physical examinations will be reported as AEs.

Analyses of safety data will be based on the Safety Set. Baseline is defined as the last non-missing result prior to the first dose of ISIS 396443 or the first sham procedure.

### 6.1 Clinical adverse events

All adverse events (AEs) will be analyzed based on the principle of treatment emergence. An adverse event will be regarded as treatment-emergent if it was present prior to receiving the first dose of ISIS 396443 or first sham procedure and subsequently worsened in severity, or was not present prior to receiving the first dose of ISIS 396443 or first sham procedure but subsequently appeared.

In the situation where change in severity (but no change in seriousness) occurs for an adverse event, study sites are instructed to enter an end date and start a new record for the adverse event. In the new record, the changed severity is to be recorded and the start date will be set to be the end date of the previous record. Data linking those records are collected in the data base. Consider three scenarios:

- The first AE record occurs prior to the first dose, the second AE record occurs on or after the first dose, and the severity increases: Only the second record will be counted as treatment-emergent.
- The first AE record occurs prior to the first dose, the second AE record occurs on or after the first dose, and the severity decreases: Neither record will be counted as treatment-emergent.
- Both records occur on or after the first dose: If the AE severity on the second record is worse than the severity on the first record, then count both records as treatment-emergent. But, if the severity improves, then only count the first record as treatment-emergent.

Of note, when counting the total number of treatment-emergent events, events linked through change in severity will still be counted as separate events.

For events with missing start or stop dates, the following criteria will be used for the purpose of identifying treatment-emergent adverse events:

- if both the start and stop dates for a particular event are missing, then the event is considered to have occurred on or after the first dose or sham procedure;

- if the start date for a particular event is missing and the stop date/time falls after the first dose or first sham procedure date/time, then the event is considered to have occurred on or after the first dose or sham procedure;
- if the start time is missing and the start date is same as the first dosing or first sham procedure date, then the event is considered to have occurred on or after the first dose or sham procedure.
- If it cannot be determined whether or not an event has occurred on or after dosing due to a missing or partial date, then the event will be assumed to have occurred on or after the first dose for the purpose of identifying treatment-emergent adverse events.

Specifically, let AESTDT denote the start date of an adverse event and TRTSTDT be the start date of treatment/sham procedure. For the purpose of identifying treatment emergent adverse events, the following algorithm will be used for the imputation of missing or partial date:

- If AESTDT is completely missing or the year is missing, then impute AESTDT to TRTSTDT.
- If, in AESTDT, year is present and month/day are missing and year is equal to the year portion of TRTSTDT, then impute the month/day portion of AESTDT to the month/day portion of TRTSTDT.
- If, in AESTDT, year is present and month/day are missing and year is not equal to the year portion of TRTSTDT, then impute the month/day portion of AESTDT to January 01.
- Consider the situation in AESTDT where year and month are present with only day missing. If the year and month are the same as those for TRTSTDT, then impute day in AESTDT with day in TRTSTDT. Otherwise, impute the day in AESTDT with the first day of the month.

It is important to emphasize that the imputed date will not be used for calculations such as onset and duration of an adverse event.

Due to the long half-life of ISIS 396443, analyses of treatment-emergent adverse events will include all events reported during the study.

Adverse events will be coded using the MedDRA dictionary. This coding system provides more than five levels to classify adverse events. In general, adverse events will be presented by system organ class and preferred terms but other classifications may be used if warranted.

The incidence of treatment-emergent adverse events will be summarized by treatment group and overall. A subject having the same adverse event more than once will be counted only once in the incidence for that adverse event. The summary tables will include incidence estimates for overall system organ class as well as for preferred terms within each system organ class. Incidence will be presented by decreasing order by system organ class and by decreasing order by preferred term within each system organ class. The most common

adverse events, i.e., those that occurred in at least 5% of subjects in either treatment group, will be presented. In addition, adverse events that occurred with an incidence 5% or higher in the ISIS 396443 group than in the control group will be presented. Upon examination of the actual data, different cut-offs may be used if it is deemed more appropriate.

#### **6.1.2 Adverse events by severity**

The investigator is to record the severity of each adverse event as mild, moderate, or severe. If a subject experiences the same adverse event multiple times, the event with the worst severity will be counted. For each treatment group, the incidence within each category will be presented. The incidence of severe events will be summarized by treatment group.

#### **6.1.3 Adverse events by relationship to study treatment**

The investigator is to record the degree to which each adverse event is related to study drug (not related, unlikely or remotely related, possibly related, and related). If a subject experiences the same adverse event multiple times, the event with the strongest relationship to study drug will be counted. For each treatment group, the incidence within each category will be presented. The incidence of drug-related events (those categorized as possibly related or related) will be summarized by treatment group.

#### **6.1.4 Serious adverse events**

The incidence of treatment-emergent serious adverse events will be summarized by treatment group. All serious adverse events will be listed including any that occurred prior to commencement of study treatment. Similar tables will be generated for adverse events that led to discontinuation of study treatment and those that led to withdrawal from the study.

#### **6.1.5 Deaths**

All adverse events which led to death will be listed.

#### **6.1.6 Adverse events following dosing/sham procedure**

To examine the onset of any adverse events following dosing or the sham procedure the incidence of events that occur 0-6 hours, 6-24 hours, and 24-72 hours following dosing or sham procedure will be presented by treatment group. In addition, presentations of events

that occurred in the first 24 hours and the first 72 hours following dosing or sham procedure will be provided.

AEs potentially related to LP occurring within 7 days of dosing, such as the PTs headache and back pain will be summarized.

For identifying adverse events following dosing or the sham procedure, the algorithm in Section 6.1 for the imputation of missing or partial start dates will be used. If time is missing and the event occurs on the same day as the day for dosing/sham procedure, the time for the dosing/sham procedure will be used as the imputed time.

#### **6.1.7 Adverse events by anti-ISIS 396443 antibody status**

To determine the impact of the formation of anti-ISIS 396443 antibodies on the safety of ISIS 396443, the incidence of adverse events in those ‘persistently’ positive, ‘transiently’ positive, and antibody negative will be presented. The definition of persistence is given in [Section 8](#).

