The PPS will include the subset of the ITT who complete at least the initial 3 doses of study drug/sham procedures, have baseline and Day 169 efficacy assessments and who have no significant protocol deviations that would be expected to affect efficacy assessments.

Significant protocol deviations will be determined prior to database lock but will include subjects who had onset of signs and symptoms consistent with SMA at less than or equal to 6 months of age, who cannot sit independently, whose HFMSE is <10 or >54 at screening, who had respiratory insufficiency at Screening (defined as medical necessity for invasive or non-invasive ventilation for >6 hours during a 24-hour period), and subjects who took any medicines (such as valproate, riluzole, creatine, sodium phenylbutyrate, hydroxyurea, salbutamol, olesoxime) during the study for the treatment of SMA, shown to modulate SMN gene expression or SMA disease progression in humans or preclinical models. The Safety Set, comprised of all subjects who were randomized and received at least one dose of study drug or underwent one sham procedure, will be used for the analysis of safety data. Subjects

randomized to receive sham procedure, incorrectly treated with ISIS 396443 will be counted in the ISIS 396443 group from the first dose of ISIS 396443 received.

The Pharmacokinetic Population is comprised of all subjects who were randomized and for which there is at least one evaluable post-dose/post-sham procedure pharmacokinetic sample. Analysis of immunogenicity data will also be based upon this population.

A listing denoting inclusion/exclusion of patients in all the analysis populations will be provided.

The individual sites in this multicenter study will be pooled for the purpose of statistical analysis.

Summary statistics will be presented throughout. For continuous endpoints, the summary statistics will generally include number of subjects with data, mean, standard deviation, median, minimum and maximum. For categorical endpoints, the summary statistics will generally include: number of subjects randomized and/or dosed, number of subjects with data, and the percentage of those with data in each category. Frequency distributions will be presented as appropriate.

The statistical software, SAS® version 9.3 or above, will be used for all summaries and statistical analyses.

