## 8 Immunogenicity data

Immunogenicity (IM) testing (anti-ISIS 396443 antibody positivity), using designated plasma samples collected from each study subject, is planned to be conducted and reported.

Immunogenicity plasma samples are to be collected pre-dosing on Days 1, 29, 85, and 274, and on Day 169 and 456. Plasma samples collected at other time points for ISIS 396443 concentration determinations may also be evaluated for IM testing if of further interest and deemed warranted by the pharmacokinetic scientist. An individual sample result will be designated 'antibody positive' based on both positive screening and confirmation assay results (i.e., confirmed positive result), and otherwise will be deemed 'antibody negative'. A study subject will be given 'antibody positive' status if they have at least one confirmed positive sample result at any time during the treatment or post-treatment evaluation periods. A study subject will be given 'antibody negative' status if all evaluated IM sample results are antibody negative and they have at least one evaluable IM result from Day 85 or later during the treatment and post-treatment evaluation periods. Otherwise, a study subject will be given 'antibody inconclusive' status.

The IM incidence and IM incidence rate at each evaluated study time point, and for the overall treatment and post-treatment evaluation period, will be determined and appropriately

summarized, by treatment, as the number of and percentage of evaluated subjects with antibody negative, antibody positive, and antibody inconclusive status. In addition, in antibody positive study subjects, antibody titers of any antibody positive samples will be reported (listed) and also appropriately summarized across subjects and by treatment (e.g., at each evaluated time point, or by observed peak titer values, etc.) at the discretion of the designated study pharmacokineticist and/or statistician.

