Antibody positivity in anti-ISIS 396443 antibody-positive subjects will also be designated (when possible) as being either ‘persistent’ or ‘transient’, but only for those subjects in which at least one confirmed antibody positive sample result is followed (>100 days later) by at least one additional IM sample assessment (which can be either a confirmed positive or negative result(s)). Those study patients meeting the above criteria and with at least 2 confirmed positive IM results occurring greater than 100 days apart (~5 immunoglobulin half-lives) will be considered to have a ‘persistent’ antibody response. All other subjects meeting the above criteria will be considered to have a ‘transient’ antibody response. Those remaining anti-ISIS 396443 antibody-positive subjects who do not meet the above criteria will not be classified as either ‘persistent’ or ‘transient’, and thus will be given the designation ‘ND’ (not determinable) for persistent/transient IM status.

When and where warranted, PK (e.g., elevated plasma trough level) and selected safety and efficacy (e.g., HFMSE) results may be further summarized (stratified) by antibody status (antibody negative versus positive subjects) and treatment. In previous clinical trials, only minimal immunogenicity samples have confirmed positive for anti-ISIS 396443 antibodies, therefore, if no, or minimal, patients are designated ‘antibody positive’ stratification by antibody status will not be summarized.

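### SAP 6.1.7 compares adverse events across fixed antibody labels, so the positive columns mix events from before and after antibodies were detected

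*SAP*

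**What the plan says.** Four parts of the SAP determine what this table will contain.

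- **Planned table (SAP 6.1.7).** The stated aim is "To determine the impact of the formation of anti-ISIS 396443 antibodies on the safety of ISIS" 396443. To meet it, "the incidence of adverse events in those ‘persistently’ positive, ‘transiently’ positive, and antibody negative will be presented". No time window and no treatment arm is named. The matching line in SAP 6.1.9 adds a listing but no window.
- **Events counted (SAP 6.1).** Because the drug has a long half-life, "analyses of treatment-emergent adverse events will include all events reported during the study". A child who has the same event more than once contributes once to its incidence. The general rule is to show incidence for each treatment group and for all subjects combined.
- **Antibody label (SAP 8).** A child is antibody positive "if they have at least one confirmed positive sample result at any time during the treatment or post-treatment evaluation periods". Persistent status goes to children "with at least 2 confirmed positive IM results occurring greater than 100 days apart (~5 immunoglobulin half-lives"). Transient status also needs a further sample more than 100 days after a positive one. Negative status needs at least one evaluable result from Day 85 or later.
- **Sampling (SAP 8).** "Immunogenicity plasma samples are to be collected pre-dosing on Days 1, 29, 85, and 274, and on Day 169 and 456". Testing is planned "using designated plasma samples collected from each study subject", so both arms are tested.

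SAP 8 also says that selected safety results may be shown by antibody status and arm together. It drops the stratification if there are no positives or only minimal numbers.

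**The concern.** The purpose is causal: what antibody formation does to safety. The comparison, however, uses a label fixed for the whole study from information that may arrive late, and attaches every event since the first dose to it. An event soon after the first lumbar puncture in a child who first tests positive on Day 274 lands in an antibody-positive column.

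The once-per-child rule sharpens this. If a child has a headache after the Day 1 procedure and another after antibodies are detected, the headache cell is already filled and the later event adds nothing. The incidence figure cannot separate the two periods.

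The risk runs both ways. Early procedure-related events can look antibody-associated, and a real effect that follows antibody formation can be blurred by events that preceded it. Follow-up also differs by label, since persistent and transient status need a sample more than 100 days after a positive one. Simple incidence does not allow for that.

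**Working it through.** The plan states no figure on this point, so there is nothing to reproduce. The size follows from its own schedule.

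**Inputs.** Antibody samples on Days 1, 29, 85, 169, 274 and 456 (SAP 8). Dosing or sham on Days 1, 29, 85 and 274 (SAP 2). Follow-up from Day 1 to Day 456 is 455 days. Arm sizes are 84 and 42 (SAP 5.1).

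**Time before antibodies.** Let d be the day of the first positive sample and p the previous scheduled sample, taken as negative. Antibodies arose somewhere between p and d.

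- Upper bound on the pre-antibody share = (d − 1)/455.
- Lower bound = (p − 1)/455.

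| First positive | Upper bound | Lower bound | Procedures before sample |
|---|---|---|---|
| Day 29 | 28/455 = 6.2% | 0/455 = 0% | 1 of 4 |
| Day 85 | 84/455 = 18.5% | 28/455 = 6.2% | 2 of 4 |
| Day 169 | 168/455 = 36.9% | 84/455 = 18.5% | 3 of 4 |
| Day 274 | 273/455 = 60.0% | 168/455 = 36.9% | 3 of 4 |

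A child first positive on Day 456 has no later scheduled sample. That child is not determinable under SAP 8 and falls in none of the three columns.

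**What one incidence figure hides.** Assume a constant event rate and no antibody effect, with study-long incidence q. For a first positive on Day 274, the chance of an event before that sample is 1 − (1 − q)^(273/455), and after it 1 − (1 − q)^(182/455). With q = 30% these are 19.3% and 13.3%. With q = 60% they are 42.3% and 30.7%. Under this assumption the pre-sample period carries the larger chance. The values of q are assumptions; the documents give none.

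**Sham children, only if arms are combined.** Suppose k of the 84 treated children are positive, all others are negative, and all 42 sham children are negative. The sham share of the negative column is then 42/(126 − k).

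- k = 2: 42/124 = 33.9%
- k = 5: 42/121 = 34.7%
- k = 15: 42/111 = 37.8%

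With k = 5, no antibody effect, and assumed event rates of 30% on drug and 10% on sham, the combined negative column shows (79 × 0.30 + 42 × 0.10)/121 = 23.1%, against 30% in positives. That is a spurious gap of 6.9 points. With 20% and 10% the gap is 3.5 points. Within the drug arm it is zero.

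**The case against.** Several points on the other side are sound.

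- **Arm.** A reader might infer that sham children would make up about a third of the antibody-negative comparator. The documents do not support that as the plan. SAP 6.1 shows treatment-emergent events for each arm as well as overall, and SAP 8 describes antibody status crossed with treatment. The SAP 3 sentence "Analysis of immunogenicity data will also be based upon this population" governs the immunogenicity analyses; SAP 6 puts safety analyses on the Safety Set. What remains is that 6.1.7 does not repeat the split, SAP 8 makes it optional, and the overall column would still mix the arms.
- **Timing.** A reader might take the 6% to 60% as time when antibodies were certainly absent. With samples 4 to 26 weeks apart, antibodies may form well before the sample that detects them, so those figures are upper bounds. They are also shares of time, not of events.
- **Usefulness.** A reader might conclude that the table can say nothing about antibodies and safety. That goes too far. It is descriptive, SAP 6.1.9 rules out significance tests on adverse events, and the listing may allow timing to be checked child by child. SAP 6.1.1 and 6.1.6 show events by onset interval and by time since dosing, although not by antibody status.
- **Relevance.** SAP 8 reports few confirmed positive samples in earlier trials, so the table may not be produced.

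These points limit the size of the problem. None links event onset to the antibody date.

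**Conclusion.** The timing point holds and is minor. As written, the positive columns combine events from before and after detection. For a classifiable child, between 0% and 37% of follow-up at the lower bound, and between 6% and 60% at the upper bound, precedes antibodies, depending on when the first positive falls. The bounds assume full follow-up to Day 456, samples on their scheduled days and a negative previous sample. No average is offered, because the documents do not say when first positives are likely.

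The arm question is a gap in wording. Dilution by sham children arises only in an overall or pooled column. All of this depends on enough positives for the table to be produced. If it is produced with few of them, one or two misplaced events can visibly change a column.

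**What to change.** In SAP 6.1.7:

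1. State that the table is based on the ISIS 396443 arm.
2. Keep the columns of all treatment-emergent events.
3. For antibody-positive children, add events with onset before, and on or after, the first confirmed positive post-dose sample, per subject-year, next to treated antibody-negative children. Since three of the four procedures fall by Day 85, the 90-day onset intervals of SAP 6.1.1 can help line up the periods compared.
4. Note that the first positive sample is a late marker of antibody onset. A sensitivity display can split at the last negative sample instead.
5. Say where children with not-determinable or inconclusive status are shown, since the table has no column for them.

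The cost is a few sentences and the programming of one descriptive table. Event onset is already classified elsewhere in SAP 6.1, with a rule for partial dates that can be reused. The downside is sparse cells, which keeping the existing columns offsets.

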### **2.4 Schedule of procedures**

Day 1 is considered to be the day when the first dose of ISIS 396443 is administered or when the first sham procedure is performed. Subjects are to return to the clinic 4 weeks later on Day 29 ( $\pm 1$  day), 12 weeks later on Day 85 ( $\pm 2$  days), 13 weeks later on Day 92 ( $\pm 1$  day), 24 weeks later on Day 169 ( $\pm 2$  days), 39 weeks later on Day 274 ( $\pm 7$  days), 12 months later on Day 365 ( $\pm 7$  days), and 15 months later on Day 456 ( $\pm 7$  days) for final follow-up.

The schedule of events follows.

Subjects will also be monitored through phone contact on Study Days 8, 56, 113, 141, 204, 239, 302, 330, 393, 421 (all  $\pm$  2 days)

Study Period	Screen	Treatment/Follow-up														D275	D365 ( $\pm$ 7D) and D456 ( $\pm$ 7D) and Early Term/ EODBP		
		D1			D2	D29 ( $\pm$ 1D)			D30	D85 ( $\pm$ 2D)			D86	D92 ( $\pm$ 1D)	D169 ( $\pm$ 2D)	D274 ( $\pm$ 7D)			
Study Day	D -28 to D -1	Pre-dose	LP/ SP	Post-dose		Pre-dose	LP/ SP	Post-dose		Pre-dose	LP/ SP	Post-dose				Pre-dose	LP/ SP	Post-dose	
Informed Consent	X																		
Inclusion/Exclusion Criteria	X																		
Medical History	X																		
Screening X-ray	X																		
Urine Pregnancy Test 	X																X 		
SMN2 copy Number 	X																		
Study Drug Injection/Sham Procedure			X			X 				X 						X 			
In-Patient Stay (24 hours)				X															
Vital Signs 	X	X		4X 	X 	X		4X 	X	X		4X 	X	X	X		4X 	X	X
Weight	X	X				X				X				X	X	X			X
Height/ulnar length	X																	X 	
Physical Examination	X	X				X				X				X	X	X			X
Neurological Examination	X	X		X 	X 	X		X 	X	X		X 	X	X	X		X 	X	X
ECG	X					X			X					X				X 	
Safety Labs 	X	X			X	X				X					X	X			X 
Coagulation Labs	X																		
Immunogenicity		X				X				X					X	X			X 

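### The adverse-event table by antibody status has no place for antibody-positive subjects labelled ND, or for antibody-inconclusive subjects

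*SAP*

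**What the plan says.** SAP 6.1.7 gives the purpose of the table: "To determine the impact of the formation of anti-ISIS 396443 antibodies on the safety of ISIS 396443". It names three groups (persistently positive, transiently positive, antibody negative) whose adverse-event incidence is to be shown, the sentence ending "positive, and antibody negative will be presented". For the meaning of persistence it refers to SAP 8.

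SAP 8 sets the sampling calendar: "plasma samples are to be collected pre-dosing on Days 1, 29, 85, and 274, and on Day 169 and 456". A subject is antibody positive "if they have at least one confirmed positive sample result at any time during the treatment or post-treatment evaluation periods". A subject is negative only if every evaluated sample is negative and at least one evaluable result dates from Day 85 or later. Anyone else is inconclusive.

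The split of positives comes next. A positive can be labelled persistent or transient only where it "is followed (>100 days later) by at least one additional IM sample assessment". Within that set, persistent means "at least 2 confirmed positive IM results occurring greater than 100 days apart", and the rest are transient. Of the positives outside that set, SAP 8 says that "subjects who do not meet the above criteria will not be classified as either" persistent or transient; they are given the designation ND.

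SAP 6.1.9 repeats the presentation by antibody status, with a listing, but names no groups. SAP 8 also allows an optional summary of selected safety results for positive against negative subjects, and it drops stratification by antibody status if positives are absent or minimal.

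**The concern.** The SAP defines five classes (persistent, transient, ND, negative, inconclusive) and then builds the one safety table that depends on them from three. ND subjects are confirmed antibody positives. Followed as written, SAP 6.1.7 shows them neither among the positives nor among the negatives.

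Membership of ND is not random. It is fixed by how late the first positive comes relative to the subject's last sample, so the table leaves out positives by the timing of their response and by length of follow-up. With few positives expected, losing even one or two could change what the table shows. If the gap is found only after unblinding, someone must decide where these subjects go with the results in view.

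**Working it through.** No sample size or error rate enters here. The check applies the SAP 8 definitions to the sampling calendar.

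**Inputs.** Post-baseline samples on Days 29, 85, 169, 274 and 456 (SAP 8), with Day 1 taken as negative. Windows of ±1, ±2, ±2, ±7 and ±7 days (SAP 2.4, which for example places a visit "39 weeks later on Day 274").

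**Rule.** Let *f* be the day of the first confirmed positive and *l* the day of the last evaluable sample. The longest interval from any positive to a later sample is *l* − *f*. A positive subject is therefore ND exactly when *l* − *f* ≤ 100.

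**Full schedule (*l* = 456).** Five samples give 2^5 = 32 patterns, of which 1 is all negative and 31 are positive.
- Persistent requires two positives more than 100 days apart. The positive patterns that fail this are the 5 with a single positive and the 2 pairs with short gaps: Days 29 and 85 (56 days) and Days 85 and 169 (84 days). Any three positives span at least 169 − 29 = 140 days. Persistent: 31 − 5 − 2 = 24.
- Of the other 7, only the pattern positive at Day 456 alone has *l* − *f* = 0. Transient: 6. ND: 1.
- Check: 1 + 24 + 6 + 1 = 32. The three groups hold 30 of the 31 positive patterns.

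**Shorter follow-up.**

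| Last sample | First positive | Gap in days, nominal (window range) | Class of the positive |
|---|---|---|---|
| Day 456 | Day 274 | 182 (168–196) | persistent or transient |
| Day 274 | Day 274 | 0 | ND |
| Day 274 | Day 169 | 105 (96–114) | persistent or transient at nominal days; ND if the actual gap is 100 or less |
| Day 274 | Day 85 | 189 (180–198) | persistent or transient |
| Day 169 | Day 169 | 0 | ND |
| Day 169 | Day 85 | 84 (80–88) | ND |
| Day 169 | Day 29 | 140 (137–143) | persistent or transient |
| Day 85 | Day 29 or 85 | 56 (53–59) or 0 | ND |
| Day 29 | Day 29 | 0 | ND |

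**Early stop of the study.** SAP 5.2 has all Day 456 assessments done at the end-of-double-blind-period (EODBP) visit, which may come as soon as 2 weeks after the last procedure. A subject first positive in the Day 274 pre-dose sample could then have *l* − *f* = 14 and be ND. If the visit falls more than 100 days after the first positive, the subject is classified.

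**Inconclusive.** A subject never positive, with no evaluable result from Day 85 on, is inconclusive and also has no group in SAP 6.1.7.

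**Could extra testing fill the gap?** SAP 8 allows plasma taken for drug concentrations to be tested as well. Protocol Appendix C has no plasma sample after Day 456, so this cannot classify a subject first positive on that day.

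These are counts of patterns. They say which subjects are omitted, not how many.

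**The case against.** The case that this is minor has several parts.

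- **Other presentations may hold ND subjects.** SAP 8 treats antibody status as positive, negative or inconclusive, and an ND subject is positive. Read with that, the SAP 6.1.9 item could accommodate them, and the optional positive-versus-negative summary would include them. This stands in part. But the optional summary is discretionary, and SAP 6.1.9 names no groups and does not override the three in SAP 6.1.7. Two programmers could produce different tables.
- **Their events are not lost to reporting.** This stands: ND subjects remain in all the overall adverse-event tables for the Safety Set. The omission concerns the antibody comparison only.
- **The table may never be made.** This stands. SAP 8 reports that few samples were positive in previous trials and drops stratification if positives are minimal. It does not define minimal.
- **A first positive at Day 456 says little about antibody effects.** The last dose is on Day 274, conversion lies somewhere in the following 182 days, and event recording stops at the last visit (Protocol 9.4.2). Much of the subject's record precedes conversion. That is a fair reason to keep ND visible as a separate class. It is no reason to leave it out, since SAP 6.1.7 does not restrict events by their timing for any group.

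A reader might also infer that an early stop leaves most children without a closing sample. The documents do not support this: immunogenicity is a Day 456 assessment, and all of those are scheduled at the EODBP visit. The problem there is only a possibly short gap.

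**Conclusion.** The point holds for the table as SAP 6.1.7 defines it. Confirmed positives labelled ND and inconclusive subjects have no place in it. On the full schedule the omission is exactly one positive pattern, positive only at Day 456. Early withdrawal, or an EODBP sample 100 days or less after the first positive, adds others.

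The number of subjects cannot be estimated. A reader might take the share of follow-up after Day 274 (182 of 455 days) as the share of positives omitted; that needs seroconversion to be uniform over time, which nothing in the documents supports. Nor does the expected number without a Month 15 visit at the interim (126 − 52 = 74) estimate it. That figure counts all children, many positives among them would be classifiable, and the SAP does not say this table is produced at the interim.

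Because the Day 169 to Day 274 gap can fall on either side of 100 days, a reader might also want the rule applied to nominal days. SAP 8 bases the cut on elapsed time, about five immunoglobulin half-lives, so this point gives no ground for changing it.

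The consequence is modest: a descriptive, untested and conditional safety table that, if made, would omit some of the subjects it is meant to describe. The primary endpoint is unaffected.

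**What to change.** In SAP 6.1.7, and in the matching item of SAP 6.1.9, make any antibody positive and antibody negative the main columns. Show persistent, transient and ND as sub-columns of the positives, and show inconclusive subjects separately. Every subject with an assigned status then has a place, and all 31 positive patterns are counted. The definitions in SAP 8, including the 100-day rule, stay as they are.

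The cost is a sentence or two in the SAP and a few table columns, with no new data or sampling. It should be settled before unblinding so that the placement of ND subjects is not chosen with the results known.
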